Methodology: This is a long-term extension study of tildrakizumab in subjects with PsA who have previously completed the treatment period of study with tildrakizumab. The eligible subjects will continue to be administered one of the following dose regimens – 200 mg Q4W, 200 mg Q12W or 100 mg Q12W to maintain the blind of the ongoing parent study to at least Week 52. Thereafter, all subjects begin migrating to receive 100 mg tildrakizumab SC injection Q12 weeks in an open-label fashion for up to an additional 4 years in this long-term extension study, provided that they meet clinical response criteria. No randomization will occur for this long-term extension study. Treatment allocation will be based upon the dose regimen assigned at the end of the treatment period in the parent study with all subjects receiving tildrakizumab. With this amendment, all subjects shall receive 100 mg tildrakizumab, every (Q) 12 weeks in the long-term extension study. All subjects who meet the inclusion criteria and complete the parent study treatment (up to Week 48 for the parent Phase 2 study, with return for the End of Treatment [EoT] visit at Week 52), and who meet defined clinical response criteria will receive 100 mg tildrakizumab, Q12 weeks for up to an additional 4 years. Subjects who completed the treatment period of their parent study and entered the parent study wash-out phase prior to study site activation of the long-term extension protocol will also be eligible for inclusion in the long-term study (when available) provided all eligibility criteria are met.				

Name of Sponsor/Company: Sun Pharma Global FZE	Individual Study Table Referring to Part of the Dossier:	(For National Authority Use Only)
Name of Product: Tildrakizumab		
Name of Active Ingredient: Tildrakizumab	Volume:	
	Page:	

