
The study will consist of a Baseline visit (Week 0) which will be the same as Week 52 of the parent study 12-weekly visits (from Week 8) up to approximately 2 years from the start of the extension study, followed by 24-weekly visits thereafter (from Week 104) up until approximately 4 years after the start of the study (approximately 5 years from the start of the parent study).
 
The parent Phase 2 study will retain a blind status at the time of the initiation of the extension study (double-blind for the PsA study, i.e., only the Sponsor and designated contract research organization [CRO] team members not directly related to the clinical conduct of the study will have been unblinded). Safety assessments will be conducted at the 12 weekly or 24-weekly visits in accordance with the Schedule of Assessments.
 
All scheduled visits will occur at the study site. However, should unusual circumstances such as public health emergency (i.e. pandemic with an infectious agent) or natural disasters arise, video conference or teleconference between the subject and site investigator will be permitted as deemed appropriate by the Sponsor provided no physical examination is needed for the visit. In this unusual circumstance, self-injection made by the subject at subject's home is allowed in order to guarantee treatment continuity.
 
When all subjects have completed the PsA parent Phase 2 study, the blind will no longer need to be maintained for the cohort, and this long-term extension study will have the option to become open-label for those subjects. Note: the timing of switch to an open-label design may differ across the cohorts of subjects entered, depending on the parent study. If other studies are also included in the long-term extension study, similar considerations for maintenance of blind will be necessary. Those subjects will be entered as separate cohorts and procedures such as continued double-dummy dosing regimens will be utilized, even after other parent Phase 2 cohorts have the option to switch to open-label.
 
Subjects not deriving sufficient clinical benefit in the opinion of the Investigator at any time after the initiation of this long-term extension study should be discontinued from investigational medicinal product (IMP), and receive clinical care as determined by the Investigator.
 
With the exception of those who withdraw informed consent, subjects who withdraw from IMP during the long-term extension study will undergo the EoT assessments approximately 4 weeks after their last administration of IMP. Subjects who complete treatment to Week 200 will return for a Follow-up assessment at Week 208 (4 years).
 
No independent assessor is needed to assess efficacy measurements. There will be no efficacy assessments during the LTE study. The Principal Investigator (PI)/designee will be responsible for performing safety evaluations.
 
Clinical Adjudication Committee will be established to evaluate cardiovascular events.
 
End of study is defined as the last visit of the 4-year treatment period (Week 208, EoT/Follow-up) for the last global subject.
		

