To date, tildrakizumab has been well tolerated at doses up to 200 mg Q12 weeks and no dose -related toxicities have been observed. The available accrued safety data from Phase 1 to Phase 3 studies in subjects with PsO supports the continued conduct of the long-term extension studies in PsO, and further study of tildrakizumab in subjects with moderate-to-severe chronic plaque PsO at doses up to and including 200 mg SC. In PsA Phase 2 study, there was no statistical advantage of therapeutic efficacy observed in a higher dose of tildrakizumab 200 mg over tildrakizumab 100 mg. Therefore, the dose regimen of tildrakizumab 100 mg, Q12 weeks was chosen for the long-term extension study. The current data also support the conduct of clinical studies in-patient populations where IL-23 is anticipated to play a pathogenic role in inflammatory disease such as PsA, AS, and related conditions.

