## Statistical Analysis Plan (SAP)

A decision to remove 1 or more treatment arms from the long-term extension study may occur as information from the parent study becomes available. Subjects already enrolled in the long-term extension study may be switched to selected dose regimens for continued evaluation at that time. This decision is anticipated to occur approximately 1 year after the start of the long-term study.

When all subjects have completed the PsA parent Phase 2 study, the blind will no longer need to be maintained for that cohort, and this long-term extension study will have the option to become open-label for those subjects. At that time, the dummy placebo administration will be removed. Note: the timing of switch to an open-label design may differ across the cohorts of subjects entered, dependent on the parent study. If other studies are also included in the long-term extension study, similar considerations for maintenance of blind will be necessary. Those subjects will be entered as separate cohorts and procedures such as continued double-dummy dosing regimens will be utilized, even after other parent Phase 2 cohorts have the option to switch to open-label.

In PsA Phase 2 study [CLR\_16\_23 PsA study], both tildrakizumab, 200 mg q12 weeks and tildrakizumab 100 mg, q12 weeks provided similar efficacies in the ACR20, ACR50, and ACR70 at Week 24. The lowest dose of 20 mg q12 weeks, did not demonstrate superiority over placebo in ACR70 and had numerically lowest ACR50 response rate among the active doses tested. The highest dose of tildrakizumab 200 mg q4 weeks, did not provide significant benefit over tildrakizumab 200 mg, q12 weeks. Therefore, the dose regimen of tildrakizumab 100 mg, q12 weeks is chosen for the long-term extension study going forward.

After all subjects switch to receive 100 mg tildrakizumab Q12W in an open-label fashion, there will be no efficacy assessments and the primary focus is the long-term safety of tildrakizumab.

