# Statistical Analysis Plan (SAP)

- Subjects Screened
- Screen Failure(s)
- All Subjects as Treated (ASaT)

The number and percentage (based on ASaT) of subjects in each of the following disposition categories will be summarized overall and by treatment group:

- Completed treatment
- Prematurely discontinued the treatment and the reasons for discontinuation
- Completed study
- Prematurely discontinued the study and the reason for discontinuation

A listing will be provided for subjects who discontinued treatment or who discontinued study with reasons for discontinuation.

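### Under the SAP's timing the 200 mg groups step down to 100 mg Q12W just as response measurement stops, and no planned table splits the remaining signs of worsening disease at that switch

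*Protocol*

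**What the plan says.** **Regimens.** The protocol synopsis (Methodology) has subjects continue on "200 mg Q4W, 200 mg Q12W or 100 mg Q12W to maintain the blind" of the parent study, and then: "Thereafter, all subjects begin migrating to receive 100 mg tildrakizumab SC injection Q12 weeks in an open-label fashion". SAP 3.3 starts this migration after the last subject's Week 52 visit (or earlier termination), a study-wide trigger. SAP 3.1 and 3.2.2 place that Week 52 in the extension.

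**Response measurement.** The synopsis says "There will be no efficacy assessments during the LTE study". SAP 3.1 is narrower: "After all subjects switch to receive 100 mg tildrakizumab Q12W in an open-label fashion, there will be no efficacy assessments". SAP 8.6 still plans ACR, HAQ-DI and SF-36 summaries by visit.

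**What is still collected.** The synopsis says "Subjects not deriving sufficient clinical benefit in the opinion of the Investigator at any time after the initiation of this long-term extension study should be" taken off IMP, so loss of benefit can appear as a discontinuation. Protocol 11.1.1.1 counts worsening of a pre-existing condition as a treatment-emergent event. Concomitant medication is recorded at every visit, and hsCRP/ESR at selected visits (Table 9-1).

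**How it is tabulated.** SAP 8.3 summarises "Prematurely discontinued the treatment and the reasons for discontinuation" overall and by treatment group. SAP 8.7 groups subjects by the regimen received at the start of the extension, and SAP 8.7.1 gives exposure-adjusted event rates by that group. hsCRP/ESR are summarised by group and visit (SAP 8.6), using nominal visits (SAP 8.1). Protocol 12.3.1 had instead called for actual treatment at specific time points where applicable. The SAP says it supersedes the protocol's statistical text, and its section 10 lists no change.

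**The concern.** The step-down in dose is the main event in this extension for subjects on 200 mg, and joint assessment stops at that point. Signs of worsening disease that remain fall within the primary safety objective, but only if they can be placed before or after the change. A rate pooled over the whole extension mixes time at risk on the higher regimen, time just after the change and time long after it. If some subjects flare soon after the change, the pooled rate understates it. The 100 mg Q12W group goes through the same move to open label and to fewer visits without a dose change, yet the plan makes no comparison with it timed to the switch.

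**Working it through.** The documents give no power, event-rate or effect-size figure to reproduce, so rates below are assumptions.

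**1. Dose rate.** 200/4 = 50 mg/week; 200/12 = 16.7; 100/12 = 8.3. Ratios to 100 mg Q12W: 6, 2 and 1.

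**2. When the switch happens.**
- SAP 3.1, 3.2.2 and 3.3: after at least 52 extension weeks on the starting regimen.
- Protocol 9.1.1: starting regimens kept to at least Week 52 of the *parent* study. The footnotes to the study diagram (also carried in SAP 3.1) and Protocol 10.2.4 have subjects enter on 100 mg, that is, at extension Week 0.

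The steps below use the SAP timing. The trigger is study-wide, so the extension week at switch differs between subjects. From the planned start (about June 2018) to the amendment date (22 July 2020) is about 108 to 112 weeks. If the switch fell near that date (an assumption), the earliest entrants switched after about Week 104.

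**3. Dilution.** Assume a constant background rate, full follow-up and no depletion of susceptible subjects.

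*Excess confined to 24 weeks, over 4 years (208 weeks):* apparent ratio = 1 + (RR − 1) × 24/208.
- RR 2: 1 + 24/208 = 1.12
- RR 3: 1 + 48/208 = 1.23

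*Excess sustained to Week 200:* apparent ratio = f + (1 − f) × RR, where f = switch week/200.
- RR 2, switch at Week 52: 0.26 + 0.74 × 2 = 1.74
- RR 2, switch at Week 104: 0.52 + 0.48 × 2 = 1.48

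Under the protocol's Week 0 reading f = 0, so a sustained excess is not diluted. A 24-week excess still is, by the later follow-up.

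**4. What a split recovers.** Assume the maximum of 286 subjects in three equal groups (191 on 200 mg pooled, 95 on 100 mg), 5 events per 100 subject-years, and RR 3 for 24 weeks. Power (two-sided 0.05) is used only as a measure of information, since the SAP plans no tests.
- Unsplit, 200 weeks: ratio 1 + 2 × 24/200 = 1.24; expected events 45.5 versus 18.3; log-ratio SE = √(1/45.5 + 1/18.3) = 0.277; z = 0.215/0.277 = 0.78; power about 12%.
- 24 weeks after the switch: 191 × 24/52 = 88.2 and 95 × 24/52 = 43.8 subject-years; expected events 13.2 versus 2.2. On the rate difference, SE = √(0.15/88.2 + 0.05/43.8) = 0.053 and z = 0.10/0.053 = 1.88, power about 47%. On the log ratio, SE = 0.73 and z = 1.10/0.73 = 1.51, power about 33%.

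With about 2 expected control events both window figures are rough. An exact conditional test gives about 26%, against 9% unsplit. The direction is the same on every method.

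**5. Precision of a before-after contrast.** One group has 95.3 × 24/52 = 44 subject-years and 44 × 0.05 = 2.2 events per 24-week window. The 95% half-width for the difference in changes between two groups is 1.96 × √(4 × 0.05/44) = 0.13, or 13 per 100 subject-years against a background of 5.

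**6. hsCRP/ESR.** Protocol 9.1.3.1.2 schedules Weeks 8, 20, 56, 104, 152 and 200. For a switch between Weeks 56 and 104, the last pre-switch and first post-switch values are 48 weeks apart. With subjects switching at different extension weeks, one nominal visit can mix both states. If the SD of the change in log hsCRP is 1 (assumed), a contrast between two groups of 95 has a 95% CI factor of exp(1.96 × √(2/95)) = 1.33, which is usable.

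**The case against.** The strongest reply is that the plan already gives several partial views of the switch.
- Columns by starting regimen keep the unswitched 100 mg group separate.
- The SAP 8.9 interim analysis is set at the same trigger as the migration. Discontinuation occurs once per subject, so final minus interim counts approximate post-switch discontinuations.
- Discontinuations are listed with reasons, and adverse event listings carry treatment at onset (Protocol 12.3.1).

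These points stand. A reader might infer that harm from the switch would be lost from view entirely, or could appear only as a discontinuation, an adverse event or a raised marker. The documents support neither. A sustained excess would remain visible though attenuated, and recorded changes in concomitant medication are a further sign. The partial views are still not a prespecified summary, and the interim mainly captures pre-switch data.

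A second reply is that efficacy objectives were removed on purpose (SAP 2.3), and that the dose was chosen because "there was no statistical advantage of therapeutic efficacy observed in a higher dose of tildrakizumab 200 mg over tildrakizumab 100 mg" (Protocol 7.2.1). The removal does not reach worsening disease recorded as an adverse event. The dose rationale rests on a comparison between parent-study arms and did not test stepping responders down. A reader might put a size on the difference it leaves open, but the documents give neither the arm sizes nor the ACR20 rates.

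A third reply is that any split will be imprecise and that the 100 mg group is not a clean control. Both hold. Open-label knowledge of a dose cut can influence investigator-judged discontinuation in the 200 mg groups only.

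**Conclusion.** The gap is real and moderate. Under the SAP's timing, response measurement ends at a 6-fold or 2-fold cut in dose rate, and no planned table places the remaining signs of worsening disease before or after it. The loss depends on duration: a 24-week RR of 2 or 3 shows as about 1.12 or 1.23, while a sustained RR of 2 shows as about 1.5 to 1.7. These figures assume a constant background rate, full follow-up and a switch between extension Weeks 52 and 104. Nothing in the documents shows that the switch causes harm. A reader might also infer that a split table would settle whether it does; at about ±13 per 100 subject-years for the before-after contrast, it would not. This is a cheap improvement within the safety objective, not a flaw that undermines the study.

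**What to change.** Add one descriptive table to SAP 8.3/8.7.1, by starting regimen and by period: before the switch, and after it, with the first 24 weeks shown apart from later follow-up. The 24-week window matters: with a switch at Week 52, a 24-week doubling averaged over all 148 post-switch weeks is still only 1 + 24/148 = 1.16. Include:

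1. Treatment-emergent worsening of psoriatic arthritis or psoriasis, per 100 subject-years.
2. IMP discontinuation for insufficient benefit. A subject who stops before switching has no switch date, so end the pre-switch period for these subjects at a calendar anchor, the migration start date. Give the post-switch rate among those who switched.
3. Start or increase of permitted anti-inflammatory, corticosteroid or DMARD medication.
4. hsCRP and ESR change from the last pre-switch to the first post-switch value.

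Show the 200 mg groups, separately and pooled, against the unchanged 100 mg Q12W group with 95% CIs, labelled descriptive.

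Also reconcile the protocol statements that 100 mg Q12W starts at extension Week 0 and that the extension has no efficacy assessments (synopsis, 9.1.1, 10.2.4) with the SAP's at least 52 extension weeks on the starting regimen and its efficacy summaries (3.1, 3.2.2, 3.3, 8.6). No dose or clinical rule is proposed.

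**Cost:** SAP wording and a derived switch date, with no new assessment. **Downsides:** few events per window and so wide rate intervals; up to about 48 weeks between the paired hsCRP/ESR values; and possible bias in discontinuation from open-label knowledge of the dose cut.

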**Concomitant Medications, Supportive Care, and Study Restrictions:**

Permitted medications include:

- Acetaminophen, except within 24 hours before a scheduled study efficacy evaluation,
- Non-steroidal anti-inflammatory drugs or low potency opioids,
- Methotrexate or leflunomide. Subjects may not be receiving both treatments concomitantly,
- Oral corticosteroids (no more than 10 mg for maintenance dose),
- Non-drug therapy (including but not limited to physical therapy, massage, diet, exercise, emollients, and joint taping).

Use of and adjustment of permitted medication is permitted throughout the study per Investigator discretion and therapeutic needs of the subject.

In accordance with the parent study, subjects are prohibited from use of the following at the time of written informed consent for and during the long-term extension study:

- High potency opioid analgesics (e.g., methadone, hydromorphone, or morphine) for the treatment of arthritis (allowed for treatment of other conditions for periods of up to 2 weeks),
- Sulfasalazine,
- Systemically administered calcineurin inhibitors (e.g., cyclosporine, tacrolimus),
- Azathioprine,
- Parenteral corticosteroids including intramuscular or intra-articular administration (topical, ophthalmic, intra-nasal, and inhaled corticosteroids are permitted) for the treatment of arthritis (allowed for treatment of other conditions for periods of up to 2 weeks),
- Live vaccines.

Any prohibited treatments must be discontinued prior to IMP initiation for the long-term extension study.

Additionally, subjects must not use systemic immunosuppressive therapies including commercially available or investigational therapies for psoriasis (PsO) and/or PsA such as:

- Use of all anti-tumor necrosis factor agents, including etanercept,
- Use of B-cell and T-cell depleting/inhibiting agents,
- Use of any other commercially available or investigational biologic therapies (other than tildrakizumab) for PsO and/or PsA within 3 months or 5 half-lives (whichever is longer) prior to or during IMP in the long-term extension study,
- Use of apremilast, or other approved or investigational medications for the treatment of current condition which are not identified as permitted therapies,
- Use of secukinumab, ustekinumab, ixekizumab, brodalumab, or any drug targeting interleukin (IL)-17, IL-23, or the IL-12/IL-23-shared p40 molecule.

**Variables:**

All endpoints will be presented for the measured time points indicated in the flow diagram of the study design.

**Pharmacokinetics:** Serum tildrakizumab concentration data.

**Safety:** The following data will be collected for assessment of safety:

- AEs.

Name of Sponsor/Company: Sun Pharma Global FZE	Individual Study Table Referring to Part of the Dossier:	(For National Authority Use Only)
Name of Product: Tildrakizumab	Volume:	
Name of Active Ingredient: Tildrakizumab	Page:	

• AEs of special interest (AESIs).

• Laboratory assessments.

• Suicidal ideation and behavior (C-SSRS).

• Vital signs.

• Electrocardiogram.

• Physical examination.

• ADA to tildrakizumab.

		

Statistical Methods: The All Subjects as Treated (ASaT) population consists of all subjects who entered the long-term extension study. The ASaT is the primary population for safety/tolerability and PK analyses. The analysis will be based on the treatment subjects actually received. Safety endpoints will be analyzed descriptively. Serum tildrakizumab concentration data will be listed by individual subject and summarized by visit and tildrakizumab dose group. For all endpoints, the subjects in the parent PsA study will be summarized separately, by study and indication.
		

Date of the Protocol: 22 July 2020
		

## 6 LIST OF ABBREVIATIONS AND DEFINITION OF TERMS

ACR(20/50/70)	The proportion of subjects achieving a 20/50/70% reduction from Baseline in American College of Rheumatology response criteria
ADA	anti-drug antibodies
AE	adverse event
AESI	adverse event of special interest
ASaT	All Subjects as Treated
AUC	area under the curve
CAC	Clinical Adjudication Committee
CFR	Code of Federal Regulations
CI	confidence interval
CPMP	Committee for Proprietary Medicinal Products
CRP	C-reactive protein
C-SSRS	Columbia-Suicide Severity Rating Scale
DSMB	Data Safety Monitoring Board
ECG	Electrocardiogram
eCRF	electronic Case Report Form
EDC	electronic data capture
EoT	End of Treatment
ESR	erythrocyte sedimentation rate
EUDRACT	European Union Drug Regulatory Agency Clinical Trial
EUQPPV	European Union Qualified Person for Pharmacovigilance
FDA	Food and Drug Administration
GCP	Good Clinical Practice
HAQ-DI	Health Assessment Questionnaire Disability Index
hsCRP	high sensitivity C-reactive protein
IA	interim analysis
ICF	Informed Consent Form
IEC	Independent Ethics Committee
ICH	International Council for Harmonisation
IgG1	immunoglobulin G1
IL	Interleukin
IMP	investigational medicinal product

IRB	Institutional Review Board
IV	Intravenous
IVRS	interactive voice response service
LTE	Long-term Extension
MACE	Major Adverse Cardiovascular Events
NOAEL	no-observed-adverse-effect-level
PASI75	proportion of subjects achieving a 75% reduction from Baseline in Psoriasis Area and Severity Index
PGA	Physician Global Assessment
PI	Principal Investigator
PK	Pharmacokinetic
PQC	product quality complaint
PsA	psoriatic arthritis
PsO	Psoriasis
PT	preferred term
PtGA	Patient Global Assessment
Q	Every
QTcB	QT corrected according to Bazett's formula
QTcF	QT corrected according to the Fridericia formula
SAE	serious adverse event
SAP	Statistical Analysis Plan
SC	Subcutaneous
SD	standard deviation
SF-36	36-item Short Form
SJC44	swollen joint count of 44 joints
SOP	Standard Operating Procedure
TB	Tuberculosis
TEAE	Treatment-emergent adverse event
TJC46	tender joint count of 46 joints
VAS	Visual Analog Scale

